7.2.5. Physical Examination

A full physical examination or symptom-directed physical examination will be performed at the timepoints specified in the Schedule of Assessments in [Appendix 6](#).

8. SAMPLE SIZE AND DATA ANALYSIS

8.1. Determination of Sample Size

No formal statistical assessment of sample size has been conducted. The sample size chosen for this study is common in human radiolabeled studies and is considered sufficient to achieve the objectives of the study. Up to 8 subjects will be enrolled and studied as a single group in order that 6 complete the study.

8.2. Analysis Populations

8.2.1. Safety Population

The safety population will include all subjects who received a dose of radiolabeled study treatment (¹⁴C-bemcentinib).

8.2.2. Pharmacokinetic Population

The PK population will include all subjects who received a dose of radiolabeled study treatment (¹⁴C-bemcentinib) and have at least 1 valid PK concentration.

8.2.3. All Subjects Population

The all subjects population will include all subjects who signed the ICF and had any study assessment recorded in the database per the protocol.

8.3. Pharmacokinetic Analyses

Pharmacokinetic parameters of bemcentinib in plasma and urine, and total radioactivity in plasma and whole blood will be determined using standard noncompartmental methods, where data allow. Full details of PK parameters will be presented in the statistical analysis plan for this study.

Pharmacokinetic parameters will be listed and summarized. No formal statistical analysis will be performed.

The mass balance recovery of total radioactivity (percentage of the dose administered recovered in urine, feces, and total excreta) will be calculated by the radioanalysis laboratory.

8.4. Safety Analysis

Safety parameters will be listed and summarized. No formal statistical analysis of safety data is planned. Each AE will be coded using the Medical Dictionary for Regulatory Activities.

8.5. Interim Analysis

No formal interim analyses are planned for this study.

10. APPENDICES

Appendix 1: Adverse Event Reporting

Definitions

An adverse event (AE) is any untoward medical occurrence in a patient or clinical investigation subject administered a pharmaceutical product, which does not necessarily have a causal relationship with this treatment. An AE can therefore be any unfavorable and/or unintended sign (including a clinically significant abnormal laboratory finding), symptom, or disease temporally associated with the use of a study treatment, whether or not related to the study treatment.

Assessment of Severity

The investigator (or designee) will be asked to provide an assessment of the severity of the AE using the following categories:

- **Mild:** Usually transient and may require only minimal treatment or therapeutic intervention. The event does not generally interfere with usual activities of daily living.
- **Moderate:** Usually alleviated with additional specific therapeutic intervention. The event interferes with usual activities of daily living, causing discomfort but poses no significant or permanent risk of harm to the subject.
- **Severe:** Interrupts usual activities of daily living, significantly affects clinical status, or may require intensive therapeutic intervention.

Relationship to Study Treatment

The investigator (or designee) will make a determination of the relationship of the AE to the study treatment using a 4-category system according to the following guidelines:

- **Not Related:** The AE is definitely caused by the subject's clinical state or the study procedure/conditions.
- **Unlikely Related:** The temporal association between the AE and the drug is such that the drug is not likely to have any reasonable association with the AE.
- **Possibly Related:** The AE follows a reasonable temporal sequence from the time of drug administration but could have been produced by the subject's clinical state or the study procedures/conditions.
- **Related:** The AE follows a reasonable temporal sequence from administration of the drug, abates upon discontinuation of the drug, follows a known or hypothesized cause-effect relationship, and (if appropriate) reappears when the drug is reintroduced.

Follow-up of Adverse Events

Every reasonable effort will be made to follow up with subjects who have AEs. Any subject who has an ongoing AE that is possibly related or related to the investigational medicinal product (IMP) or study procedures at discharge will be followed up, where possible, until

resolution or until the unresolved AE is judged by the investigator (or designee) to have stabilized. This will be completed at the investigator's (or designee's) discretion. Any subject who has an ongoing AE that is not related or unlikely related to the IMP or study procedures at the discharge visit can be closed out as ongoing at the investigator's discretion.

Adverse Drug Reactions

All noxious and unintended responses to an IMP (ie, where a causal relationship between an IMP and an AE is at least a reasonable possibility) related to any dose should be considered adverse drug reactions.

For marketed medicinal products, a response to a drug which is noxious and unintended and that occurs at doses normally used in man for prophylaxis, diagnosis, or therapy of diseases or for modification of physiological function is to be considered an adverse drug reaction.

An unexpected adverse drug reaction is defined as an adverse reaction, the nature or severity of which is not consistent with the applicable product information (eg, investigator's brochure for an unapproved IMP).

Serious Adverse Events

A serious adverse event (SAE) is defined as any untoward medical occurrence that at any dose either:

- results in death
- is life-threatening
- requires inpatient hospitalization or prolongation of existing hospitalization
- results in persistent or significant disability/incapacity (disability is defined as a substantial disruption of a person's ability to conduct normal life functions)
- results in a congenital anomaly/birth defect
- results in an important medical event (see below).

Important medical events that may not result in death, be life-threatening, or require hospitalization may be considered SAEs when, based upon appropriate medical judgment, they may jeopardize the subject and may require medical or surgical intervention to prevent one of the outcomes listed in this definition.

Instances of death or congenital abnormality, if brought to the attention of the investigator at any time after cessation of the study treatment and considered by the investigator to be possibly related to the study treatment, will be reported to the sponsor.

Definition of Life-threatening

An AE is life-threatening if the subject was at immediate risk of death from the event as it occurred (ie, does not include a reaction that might have caused death if it had occurred in a more serious form). For instance, drug-induced hepatitis that resolved without evidence of

hepatic failure would not be considered life-threatening even though drug-induced hepatitis can be fatal.

Definition of Hospitalization

Adverse events requiring hospitalization should be considered serious. In general, hospitalization signifies that the subject has been detained (usually involving an overnight stay) at the hospital or emergency ward for observation and/or treatment that would not have been appropriate at the study site. When in doubt as to whether hospitalization occurred or was necessary, the AE should be considered as serious.

Hospitalization for elective surgery or routine clinical procedures, which are not the result of an AE, need not be considered AEs and should be recorded on a clinical assessment form and added to the electronic case report form. If anything untoward is reported during the procedure, this must be reported as an AE and either 'serious' or 'nonserious' attributed according to the usual criteria.

Serious Adverse Event Reporting

Serious AEs that occur between the time of signing the informed consent form and until 28 days after the dose of study treatment, regardless of relationship to the study treatment, must be reported within 24 hours of knowledge of the event to the sponsor or designee. In addition, if the investigator learns at any time of an SAE which is believed to be related to the study treatment then this must be reported to the sponsor, even if more than 28 days have elapsed since the dose of study treatment.

Serious AE reporting will be conducted as described in the safety management plan. The SAE form will collect all relevant data concerning the AE, including: details of the nature of the symptoms, time of onset, duration, and severity, together with an investigator's (or designee's) opinion of the relationship to study treatment, and any action taken in relation to the planned administration of study treatment. In addition, the investigator should provide relevant medical history, concomitant medications, laboratory or diagnostic test reports, details of any treatment for the SAE, and all other pertinent medical information.

Pregnancy

Pregnancy (paternal exposure to study treatment) does not meet the definition of an AE. However, to fulfill regulatory requirements any pregnancy should be reported following the SAE process to collect data on the outcome for both mother and fetus.

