3. INVESTIGATIONAL PLAN

3.1. Overall Study Design and Plan

This will be a Phase 1, open-label, nonrandomized, single oral dose study in healthy male subjects.

Potential subjects will be screened to assess their eligibility to enter the study within 28 days prior to dose administration. Up to 8 subjects will be enrolled to ensure that 6 subjects complete the study. Subjects will be admitted into the study site on Day -1. On the morning of Day 1, all subjects will receive a single oral dose of [REDACTED] mg containing approximately [REDACTED] μCi ([REDACTED] MBq) of ¹⁴C-bemcentinib, 30 minutes after starting a standard high-fat breakfast.

Subjects will be confined to the study site until at least Day 8. Subjects will be discharged from the study site on Day 8 if the following discharge criteria are met:

- $\geq 90\%$ mass balance recovery, and
- $<1\%$ of the total radioactive dose is recovered in combined excreta (urine and feces) in 2 consecutive 24-hour periods.

If these discharge criteria are not met by Day 8, subjects will be required to remain resident until discharge criteria are met, up to Day 15. If criteria are not met by Day 15, subjects may be asked to collect 24-hour excreta samples on up to 2 further occasions on a nonresidential basis to allow extrapolation of urinary and fecal excretion. If needed, the 2 additional 24-hour nonresidential collections will start on the morning of Days 22 and 29 (to be brought into the study site at the end of the collection interval on Days 23 and 30, respectively). If on the second occasion the subject has still not met the desired criterion, then the subject will be discharged from the study, per investigator and sponsor decision.

Subjects experiencing emesis during the first 4 hours postdose may be discharged on the same day from the study site, provided there are no safety concerns, and after discharge study procedures are performed.

The total duration of study participation for each subject (from screening to outpatient visit [if required]) is anticipated to be a maximum of approximately 58 days.

The start of the study is defined as the date the first subject signs an informed consent form (ICF). The point of enrollment occurs at the time of subject number allocation. The end of the study is defined as the date of the last subject's last assessment (scheduled or unscheduled).

A Schedule of Assessments is presented in [Appendix 6](#).

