7.2. Safety and Tolerability Assessments

7.2.1. Adverse Events

Adverse event definitions, assignment of severity and causality, and procedures for reporting SAEs are detailed in [Appendix 1](#).

The condition of each subject will be monitored from the time of signing the ICF to final discharge from the study. Subjects will be observed for any signs or symptoms and asked about their condition by open questioning, such as 'How have you been feeling since you were last asked?', at least once each day while resident at the study site and at each study visit. Subjects will also be encouraged to spontaneously report AEs occurring at any other time during the study.

Any AEs and remedial action required will be recorded in the subject's source data. The nature, time of onset, duration, and severity will be documented, together with an investigator's (or designee's) opinion of the relationship to study treatment.

Adverse events recorded during the course of the study will be followed up, where possible, until resolution or until the unresolved AEs are judged by the investigator (or designee) to have stabilized. This will be completed at the investigator's (or designee's) discretion.

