Blood pressure and pulse rate ^f	X	X	Predose and 2, 4, 8, 24, and 48 hours postdose	X	
Oral body temperature	X	X		X	
12-lead electrocardiogram	X	X	Predose and 2 and 24 hours postdose	X	
Physical examination		X		X ^k	

^a Additional 24-hour collections (urine and feces) for radioanalysis may continue up to Day 15 if mass balance recovery is not adequate or radioactivity is still being eliminated in excreta. Subjects will be discharged when the following criteria are met: ≥90% mass balance recovery and <1% of the total radioactive dose is recovered in excreta (urine and feces) in 2 consecutive 24-hour periods. If this is the case, subjects will be asked to remain resident within the clinical research unit for a further period (up until Day 15).

^b Discharge will be from Day 8 to Day 15 depending on radioactivity elimination.

^c Interim medical history.

^d On Day 1, a blood sample will be collected and stored for subsequent assessment of the pharmacogenetic profile of bemcentinib in order to explore the influence of pharmacogenetic factors on the pharmacokinetics and safety.

^e If discharge criteria (mass balance recovery) is not adequate ($\leq 90\%$ mass balance recovery, and $>1\%$ of the total radioactive dose is recovered in excreta [urine and feces] in 2 consecutive 24-hour periods) are not met by Day 8, subjects will be required to remain resident until discharge criteria are met, up to Day 15. If criteria are not met by Day 15, subjects may be asked to collect 24-hour excreta samples on up to 2 further occasions on a nonresidential basis to allow extrapolation of urinary and fecal excretion. If needed, the 2 additional 24-hour nonresidential collections will start on the morning of Days 22 and 29 (to be brought into the study site at the end of the collection interval on Days 23 and 30, respectively). If on the second occasion the subject has still not met the desired criterion, then the subject will be discharged from the study, per investigator and sponsor decision.

^f Blood pressure and pulse rate will be measured singly followed by at least 5 minutes in the supine position.

^g Plasma samples for metabolite profiling will be selected after confirming the total radioactivity time profile. Urine and fecal samples for metabolite profiling will be selected after confirming total radioactivity time profile in excreta.

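### SAEs are reportable to Day 29, but no contact is scheduled after discharge for most subjects, so AE incidence is summarized over unequal windows that depend on excretion

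*Combined protocol and SAP*

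**What the plan says.** **SAE window.** Appendix 1 (Serious Adverse Event Reporting) covers SAEs from consent "until 28 days after the dose of study treatment, regardless of relationship to the study treatment, must be reported". The duty is triggered by awareness: an event "must be reported within 24 hours of knowledge of the event to the sponsor or designee". SAEs believed to be related are reportable whenever the investigator learns of them, with no time limit.

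**Monitoring period.** Section 7.2.1: "The condition of each subject will be monitored from the time of signing the ICF to final discharge from the study". Subjects are asked about their condition "at least once each day while resident at the study site and at each study visit".

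**When subjects leave.** Section 3.1: "Subjects will be discharged from the study site on Day 8 if the following discharge criteria are met". Appendix 6, footnote b: "Discharge will be from Day 8 to Day 15 depending on radioactivity elimination". Section 3.1 adds an early exit: "Subjects experiencing emesis during the first 4 hours postdose may be discharged on the same day from the study site", on condition that there are no safety concerns and the discharge procedures have been done.

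**After discharge.** Appendix 6 has one later column with AE recording, the outpatient visit. It applies only to subjects who miss the excretion criteria by Day 15, and it is optional even for them: "subjects may be asked to collect 24-hour excreta samples on up to 2 further occasions on a nonresidential basis". The collections start on Days 22 and 29 and are returned on Days 23 and 30.

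**Analysis.** Incidence and severity of AEs is a secondary endpoint (Table 1). Section 8.4 plans descriptive summaries and names no observation window.

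**The concern.** The protocol defines a 28-day period in which any SAE counts, but does not plan to ask most subjects about the later part of it. After discharge, a new event reaches the site only if the subject volunteers it or it comes to light by chance. The clause that reaches SAEs regardless of causality depends most on asking, because subjects have little reason to report an event that they do not connect with the study.

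The second effect is on the AE summary. The length of active observation is set by how fast radioactivity leaves the body: a fast eliminator may be watched for 7 days and a slow one for up to 29. An incidence table over 6 to 8 subjects then mixes unequal observation times, and observation time is tied to drug disposition. Events that nobody asked about cannot be recovered at analysis.

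**Working it through.** **Check on the day count.** Section 3.1 gives a maximum participation of approximately 58 days. Screening of up to 28 days plus Day 30 (return of the second outpatient collection) gives 28 + 30 = 58, which reproduces the stated figure.

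**End of the SAE window.** Dose on Day 1; 28 days later is Day 1 + 28 = Day 29.

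**Gap by last scheduled contact.** Days observed = last contact day − 1. Gap = 28 − days observed, not below 0.

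| Last scheduled contact | Days observed | Gap (days) | Share of 28 days |
|---|---|---|---|
| Day 1 (same-day discharge after emesis, if used) | under 1 | about 28 | about 100% |
| Day 8 (criteria met) | 7 | 21 | 75% |
| Day 15 (criteria met) | 14 | 14 | 50% |
| Day 23 (first outpatient return only) | 22 | 6 | 21% |
| Day 30 (second outpatient return) | 29 | 0 | 0% |

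**In person-days.** With 8 subjects the window is 8 × 28 = 224 person-days. If all left on Day 8, 8 × 7 = 56 would be observed (25%). If all left on Day 15, 8 × 14 = 112 would be observed (50%). These are bounds for subjects without early emesis who meet the criteria. The documents do not say how many will leave when.

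**How likely is Day 8?** The discharge criteria are recovery of at least 90% and less than 1% of the dose in each of two consecutive 24-hour periods. As an illustration only, assume that all of the dose is excreted by a first-order process without lag, at the parent half-lives in Section 1.3 (45.6 to 88.7 h). Excretion in 24-hour interval n is (1 − r)·r^(n−1), with r = 2^(−24/half-life).

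- 45.6 h: r = 0.694. Recovery at 168 h is 92.2%, but intervals 6 and 7 still excrete 4.9% and 3.4%. Intervals 11 and 12 (0.80% and 0.55%) are the first pair below 1%, so the criteria are met about Day 13, with a gap of 28 − 12 = 16 days.
- 88.7 h: r = 0.829. Recovery at 168 h is 73.1%. At 336 h it is 92.8%, but interval 14 still excretes 1.5%, so the criteria are not met by Day 15 and the subject moves to the optional outpatient group.

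On these inputs, discharge falls late in the permitted range or beyond it. Day 8 is what the protocol allows, not what this illustration predicts. Early fecal recovery of unabsorbed dose would bring discharge forward.

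**The case against.** **There is no contradiction.** A reader might infer that Appendix 1 promises active capture to Day 29 and so conflicts with Section 7.2.1. It does not: reporting is required on knowledge of an event. The two sections can both be followed as written. This stands, and the point is about ascertainment only.

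**Contact does not cease altogether.** A reader might infer that discharged subjects are lost to view. In fact AEs ongoing at discharge and at least possibly related are followed to resolution or stability, spontaneous reports are encouraged during the study, pregnancies are reportable, and Section 4.4 lets the investigator ask a withdrawn subject to return. This also stands, but none of these provisions looks for new events in a subject who was well at discharge.

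**Day 8 leavers do not demonstrably carry much drug.** The long half-life tempts one to argue that a subject leaving on Day 8 still has a large fraction of peak plasma level. The documents do not support that pairing. The half-lives come from an earlier study conducted mainly in the fasted state, and on those same half-lives the illustration above does not release anyone on Day 8. The slowest eliminators are the ones who may be observed longest, which is a sensible feature. The case for a common window does not rest on residual drug.

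**Early emesis.** Same-day discharge is permitted, not required, and carries safety conditions. It is also worded as leaving the site, whereas Section 7.2.1 runs to final discharge from the study. Even if such a subject remains formally in the study, Appendix 6 provides no later contact.

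**Other documents and scale.** SAE reporting is to follow a safety management plan that is not available here and may add contacts. The study is small, single-arm and descriptive, and onset times are recorded, so unequal follow-up will be visible in the listings. This limits the consequence. It does not supply the missing observations.

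**Conclusion.** The point holds as a gap in scheduled ascertainment. For subjects who meet the excretion criteria between Day 8 and Day 15, 14 to 21 of the 28 days have no scheduled enquiry. After same-day discharge for emesis it is up to about 28 days. For subjects who miss the criteria by Day 15 it is 6 days after one outpatient return and 0 after both; those who are not asked to return keep the 14-day gap.

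The consequence is confined to the secondary AE endpoint and the completeness of SAE reporting: incidence is summarized over windows of unequal length that depend on excretion. The primary mass balance and PK endpoints are unaffected.

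The conclusion assumes dosing on Day 1 and that Appendix 6 lists every planned contact. If the safety management plan already contains a Day 29 contact, only the alignment of the protocol text and the choice of summary windows remain.

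**What to change.** 1. Add one row to Appendix 6: a telephone contact on Day 29 for every subject not attending the Day 29-30 visit, recording AEs, SAEs and medication.
2. State in Section 7.2.1 that AE collection runs to that contact or visit. Define this as the end of AE collection and leave the meaning of discharge alone, because the restrictions in Section 6 run until discharge and should not be lengthened by accident.
3. In Section 8.4 and the SAP, summarize AEs to Day 8 (the window shared by all who stay resident) and to Day 29 (the window shared by everyone). Both are useful, because recall by telephone is less sensitive than daily questioning.

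No change to dosing or to the discharge rules is needed.

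**Cost.** At most 8 calls and one schedule row. Participation lengthens by 29 − 15 = 14 days for a Day 15 leaver, 29 − 8 = 21 days for a Day 8 leaver, and up to about 28 days after same-day discharge. All of this lies within the stated 58-day maximum. Because the study ends at the last subject's last assessment, the end of the study may move later if the last subjects leave early.
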